5.5 Pharmacokinetic and Anti-Xa Assessments

PK and anti-Xa assessments will only be performed for patients randomized to the apixaban arm. [Table 5.5-1](#) summarizes the sampling collection schedule to be followed for these assessments.

Sparse samples for PK and PD (anti-FXa activity) will be taken in subjects receiving apixaban. Pre-dose and post dose samples of apixaban may be taken on the same day if feasible (eg, in-patients). Alternatively samples may be collected on separate days (eg, out-patients), for example, subjects may have the pre-dose sample taken before the LP procedures and the post-dose sample taken on an alternate visit.

The date and time of apixaban administration must be recorded for the dose immediately before PK/anti-FXa sample collection. Whenever possible PK/PD samples should be collected at the same time as the clinical laboratory assessments and may be drawn through the CVAD. Further sample collection and processing instructions will be provided separately.

[figure not shown]
Table 5.5-1: PK and Anti-Xa Sample Collections Schedule^a

Patient status	Day of blood sample	Time (Relative to Dosing) Hour ^a	PK and anti-Xa Blood Samples
In patient	1 day prior to LP (eg, day 7 if day 8 LP)	0 (predose) 1 - 4h (post-dose)	X
Out patient	The day of LP (any day an LP will be performed) ^b	Random sample collected prior to LP procedures	X
Out patient	15 or another day (any visit at which an LP will not be performed) ^b	Random sample collected 0.5 to 12 h after the AM dose of apixaban and prior to the PM dose	X

^a The date and time of apixaban administration must be recorded for the dose immediately preceding PK/anti-FXa sample collection.

^b

The date and time of apixaban administration for the dose immediately preceding PK/anti-FXa sample and the time of PK/Anti-FXa sample collection must be recorded.

6 ADVERSE EVENTS

Importance of Adverse Event Reporting

Timely and complete reporting of safety information assists BMS in identifying any untoward medical occurrence, thereby allowing: (1) protection of safety of study patients; (2) a greater understanding of the overall safety profile of the investigational product; (3) recognition of dose-related investigational product toxicity; (4) appropriate modification of study protocols; (5) improvements in study design or procedures; and (6) adherence to worldwide regulatory requirements.

An *Adverse Event (AE)* is defined as any new untoward medical occurrence or worsening of a pre-existing medical condition in a patient or clinical investigation subject administered an investigational (medicinal) product and that does not necessarily have a causal relationship with this treatment. An AE can, therefore, be any unfavorable and unintended sign (including an abnormal laboratory finding, for example), symptom, or disease temporally associated with the

use of investigational product, whether or not considered related to the investigational product. Adverse events can be spontaneously reported or elicited during open-ended questioning, examination, or evaluation of a subject. (In order to prevent reporting bias, subjects should not be questioned regarding the specific occurrence of one or more AEs.)

For all adverse events, including those that are serious, if the diagnosis of the underlying illness or disorder is known; this diagnosis should be recorded, rather than its individual symptoms.

All adverse events will be graded according to the NCI CTCAE version 4.0.

In this study, expected chemotherapy-related CTCAE Grade 1 or Grade 2 AEs of nausea, vomiting, anorexia, fatigue, headache, fever, neutropenia, or an institution SOC practice to extend a hospitalization for the possibility of chemotherapy induced neutropenia will **not** be collected on the non-serious AE case report form. However, any extended hospitalization due to a confirmed neutropenia or Grade 3 or higher AE/SAE of nausea, vomiting, anorexia, fatigue, fever, neutropenia, or headache **will** be collected, whether considered related to chemotherapy or not.

The following categories and definitions of causal relationship to investigational product as determined by a physician should be used for all BMS clinical study AEs:

- Related - There is a reasonable causal relationship to study drug administration and the AE.
- Not Related - There is not a reasonable causal relationship to study drug administration and the AE.

The expression "reasonable causal relationship" is meant to convey in general that there are facts (eg, evidence such as de-challenge/re-challenge) or other arguments to suggest a positive causal relationship.

AEs should be followed to resolution or stabilization, and reported as SAEs if they become serious. This also applies to patients experiencing AEs that cause interruption or discontinuation of investigational product, or those experiencing AEs that are present at the end of their participation in the study; such patients should receive post-treatment follow-up as appropriate. If an ongoing AE changes in its severity or in its perceived relationship to study drug, a new AE entry for the event should be completed.

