- To assess the effect of prophylactic apixaban versus no systemic anticoagulant during ~28 days of induction chemotherapy including asparaginase on single adjudicated endpoints of non-fatal DVT (including symptomatic and asymptomatic), PE, and CVST; and VTE-related-death.

- To assess the effect of prophylactic apixaban versus no systemic anticoagulant during ~28 days of induction chemotherapy including asparaginase on the composite endpoint of adjudicated major and clinically relevant non-major bleeding (CRNMB) events.

Study Design:

Figure -1: Study Design

Study Design:

Recruitment will start for children of ages 1 to < 18 years of age and weighing equal to or > 6 kg.

The current study is a randomized, open-label, multi-center clinical trial in which pediatric subjects will be randomized 1:1 to prophylactic apixaban for thromboembolism prevention versus no systemic anticoagulant prophylaxis during induction chemotherapy. Subjects randomized to apixaban will receive a prophylactic-dose of apixaban. While subjects ≥ 5 years may be administered either 2.5-mg, 0.5-mg tablets or oral solution apixaban, use of 2.5 mg or 0.5 mg tablets is encouraged. Subjects < 5 years and < 35 kg may be administered 0.5-mg tablets only.

Subjects will be administered apixaban twice daily by mouth or via a NGT or GT according to weight range as per below Table during approximately 28 days of induction chemotherapy including asparaginase.

Weight range	Dose
≥ 35 kg	2.5 mg twice daily
<35 to 25 kg	2 mg twice daily
<25 to 18 kg	1.5 mg twice daily
<18 to 10.5 kg	1 mg twice daily
<10.5 to 6 kg	0.5 mg twice daily

The previously communicated dosing for the body weight tier of 9 to < 12 kg has been redistributed into a 6 to < 10.5 kg weight tier and a 10.5 to < 18 kg weight tier.

Pediatric subjects randomized to apixaban should begin treatment following randomization (as long as conditions for apixaban administration are met). Study medication must be initiated prior to or within 12 hours of the first dose of asparaginase or by Day 4 \pm 3 of planned 3-4 drug systemic induction chemotherapy, whichever is first. Day 1 is the first day of planned 3-4 drug systemic induction ALL chemotherapy.

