6.2.1 Nonserious Adverse Event Collection and Reporting

The collection of nonserious AE information should begin at randomization for all patients, including the patients randomized to the usual care arm.

Nonserious AEs should be followed to resolution or stabilization, or reported as SAEs if they become serious (see [Section 6.1.1](#)). Follow-up is also required for nonserious AEs that cause interruption or discontinuation of study drug, or those that are present at the end of study treatment as appropriate. All identified nonserious AEs must be recorded and described on the nonserious AE page of the CRF (paper or electronic). Completion of supplemental CRFs may be requested for AEs and/or laboratory abnormalities that are reported/identified during the course of the study.

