7.6.2 Adverse Events

All AEs will be coded and grouped into Preferred Terms (PT) by System Organ Class (SOC), using the Medical Dictionary for Regulatory Activities (MedDRA). Listings and summaries will be based on the resulting SOCs and PTs.

The incidence of bleeding-related AEs during the Treatment Period will be summarized by SOC, PT and treatment group.

All reported AEs and SAEs will be listed, indicating the subject id, treatment group, age, gender, race, day of onset relative to start of dosing, resolution date, investigator-assessment of relationship to study drug, investigator-assessment of intensity of event, action taken regarding study drug and whether treatment was required for the event.

Summary information (the number and percentage of subjects) regarding AEs (for serious and non-serious events) will be tabulated by SOC, PT and treatment group for:

- all events
- deaths
- related events
- all events categorized by intensity

The frequency of subjects discontinuing study drug due to AEs will be tabulated by SOC, PT and treatment group.

Most common AEs (reported in more than 5% of subjects in any treatment group) will also be summarized by PT and treatment group.

Laboratory AEs are laboratory results identified by the Investigator as AEs and thus reported on the AE pages of the CRF. Any such AE occurring during the Treatment Period will be included in the respective AE summaries.

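### Low-grade events of seven common terms are collected only when not put down to chemotherapy, so the open-label by-arm AE tables can show a spurious excess on apixaban

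*Protocol*

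**What the plan says.** Protocol section 6 (Adverse Events) exempts from the non-serious AE form "expected chemotherapy-related CTCAE Grade 1 or Grade 2 AEs of nausea, vomiting, anorexia, fatigue, headache, fever, neutropenia". It also exempts hospital stays extended by local practice for possible neutropenia. The next sentence reverses this for Grade 3 or higher events of the same terms, and for extended hospitalization with confirmed neutropenia: these are collected "whether considered related to chemotherapy or not".

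Causal relationship to investigational product is to be classified in categories "as determined by a physician should be used for all BMS clinical study AEs". SAP section 7.6.2 lists "investigator-assessment of relationship to study drug". Neither document names a blinded assessor for general AEs or says how an event qualifies as expected and chemotherapy-related.

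The Protocol Synopsis states: "The current study is a randomized, open-label, multi-center clinical trial". Control is no systemic prophylaxis, without placebo. Protocol section 6.2.1 says: "The collection of nonserious AE information should begin at randomization for all patients, including the patients randomized to the usual care arm".

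SAP section 7.6.2 plans summary information "regarding AEs (for serious and non-serious events) will be tabulated by SOC, PT and treatment group", for all events, deaths, related events and events by intensity. It adds: "Most common AEs (reported in more than 5% of subjects in any treatment group) will also be summarized by PT and treatment group". The safety population (SAP section 6.3) is all randomized subjects.

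**The concern.** Both arms receive induction chemotherapy, so low-grade nausea, vomiting or headache can be expected in both. A control child with Grade 1 nausea has no study drug to blame. Unless there is another evident cause, the event will be called chemotherapy-related and not recorded. In an apixaban child, an investigator who knows the assignment may instead put the same event down to apixaban, and it then no longer falls clearly within the exemption.

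The by-arm tables would then mix a drug effect, if there is one, with a difference in what was written down. The distortion runs against apixaban. It could appear as an apparent low-grade intolerance in a paediatric safety table, or lift a term over the display threshold of the common-AE table.

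**Working it through.** **1. Does Grade 1-2 collection depend on attribution?** Two adjacent sentences of Protocol section 6 answer this. The Grade 3 or higher sentence expressly sets attribution to chemotherapy aside. The Grade 1-2 sentence carries the qualifier and has no such waiver. If the Grade 1-2 exemption were a fixed list regardless of cause, neither the qualifier nor the contrast would serve a purpose. A low-grade event outside the exemption falls under Protocol section 6.2.1, which requires all identified nonserious AEs to be recorded.

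**2. Is the dependence different by arm?** Three routes are possible for a Grade 1-2 event of these terms:

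| Cause assigned | Control | Apixaban |
|---|---|---|
| Chemotherapy | not collected | not collected |
| Other cause (e.g. infection, lumbar puncture) | collected | collected |
| Apixaban | not possible | collected |

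Only the last row differs by arm.

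**3. Does anything downstream correct it?** Blinded adjudication (SAP section 4.1) covers the efficacy components and bleeding, not these AEs. SAP section 7.6.2 has no separate rule for the seven terms.

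**4. How large could it be?** There is no stated figure to reproduce. The following inputs are assumptions, per term:
- *t*, the true Grade 1-2 incidence, equal in both arms: 30%, 50%, 70%
- *x*, the share of events on apixaban attributed to apixaban: 5%, 10%, 20%
- *o*, the share with another non-chemotherapy cause, equal in both arms: 0% or 5%
- about 250 children per arm (500 randomized 1:1, SAP section 5)

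Recorded rate in control = *t* × *o*. Recorded rate on apixaban = *t* × (*o* + *x*). Spurious excess = *t* × *x*, whatever the value of *o*.

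| *t* | *x* = 5% | *x* = 10% | *x* = 20% |
|---|---|---|---|
| 30% | 1.5 points | 3.0 | 6.0 |
| 50% | 2.5 | 5.0 | 10.0 |
| 70% | 3.5 | 7.0 | 14.0 |

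In children, the range runs from 0.015 × 250 ≈ 4 to 0.14 × 250 = 35.

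With *o* = 0, control records nothing. The middle case then gives 50% × 10% = 5.0% on apixaban, which is at the display threshold but not above it. With *o* = 5%, control records 1.5% to 3.5% and apixaban 3.0% to 17.5%. The relative risk is (*o* + *x*)/*o*, from 10/5 = 2 to 25/5 = 5, with no true difference. The middle case becomes 2.5% against 7.5%, which the common-AE table would display.

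**The case against.** The defence has several good points.

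- **Other causes.** A reader might infer that these terms would appear in the apixaban arm only. The documents do not support that: low-grade events put down to infection, lumbar puncture or another drug are collected in both arms. Only apixaban-attributed events are confined to one arm.
- **Unit of the table.** A reader might pool the seven terms, take 60% × 10% = 6 points, and set that against the 5% threshold. The table is by preferred term. Six points spread evenly over seven terms, one per child, is 6/7 ≈ 0.9% per term.
- **Significance.** A reader might infer a nominally significant safety signal. The SAP plans counts and percentages for general AEs; nominal p-values are for the bleeding endpoints. Any probability would also depend on the test. With zero control events and 250 per arm, an excess of 1.5 points reaches two-sided p < 0.05 with probability 0.52 by uncorrected chi-square but 0.18 by Fisher's test; at 3 points the figures are 0.94 and 0.76.
- **Visibility.** The SAP also tabulates related events and events by intensity, and lists both attributes for each AE. The excess consists of low-grade events judged related, so a careful reader could trace it. This stands as mitigation, but the all-events and common-AE tables would still show the uncorrected comparison.
- **Attribution may be rare or shared.** The protocol requires a reasonable causal relationship supported by facts or arguments. It does not make chemotherapy and apixaban exclusive causes: an event judged related to both is arguably still exempt. The 5-20% share has no support in the documents and could be lower.
- **Fixed-class reading.** The exemption can be read as a standing list of expected events regardless of cause, and the text does not say outright who decides. The Grade 3 or higher wording makes this the weaker reading.

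These points limit the size and certainty of the bias. They do not remove the asymmetry in the third row of the routes table.

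**Conclusion.** The collection rule is differential by arm for Grade 1-2 events of the seven terms, and the SAP compares the arms on them without allowance. The result can be a spurious excess on apixaban, not an absence in control. Its size cannot be derived from the documents: 1.5 to 14 points per term rests entirely on the assumed 30-70% incidence and 5-20% attribution, and it shrinks to nothing if investigators rarely attribute such events to apixaban alone.

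The reach is limited. The adjudicated VTE and bleeding endpoints, primary and secondary, do not use these data. SAEs and Grade 3 or higher events are collected regardless of attribution to chemotherapy. This is a cheap and worthwhile correction to the reading of the low-grade AE tables, not a threat to the trial's main conclusions.

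**What to change.** Change SAP section 7.6.2 only:

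1. For nausea, vomiting, anorexia, fatigue, headache, fever and neutropenia, base the between-arm comparison, including the common-AE table, on Grade 3 or higher events and SAEs.
2. Present the collected Grade 1-2 events of these terms in a separate table, by arm and with the investigator's attribution.
3. Footnote both: *Non-serious Grade 1-2 events of these terms were recorded only when not considered expected effects of chemotherapy; recording therefore depended on attribution and rates are not comparable between arms.*

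An alternative is to drop attribution from Protocol section 6 and stop collecting these Grade 1-2 events altogether. That would equalise the arms, but it would discard low-grade events judged related to study drug in children and sit badly with the requirement in Protocol section 6.2.1 to record all identified nonserious AEs. It should not be done.

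The cost is one extra table and its programming, with no change at sites and no loss of collected data. Low-grade events of these terms leave the main between-arm comparison, where they were not comparable.

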6.1 Serious Adverse Events

A *Serious Adverse Event (SAE)* is any untoward medical occurrence that at any dose:

- results in death
- is life-threatening (defined as an event in which the subject was at risk of death at the time of the event; it does not refer to an event which hypothetically might have caused death if it were more severe)
- requires inpatient hospitalization or causes prolongation of existing hospitalization (see **NOTE** below)
- results in persistent or significant disability/incapacity
- is a congenital anomaly/birth defect

- is an important medical event (defined as a medical event(s) that may not be immediately life-threatening or result in death or hospitalization but, based upon appropriate medical and scientific judgment, may jeopardize the subject or may require intervention [eg, medical, surgical] to prevent one of the other serious outcomes listed in the definition above.) Examples of such events include, but are not limited to, intensive treatment in an emergency room or at home for allergic bronchospasm; blood dyscrasias or convulsions that do not result in hospitalization.) Potential drug induced liver injury (DILI) is also considered an important medical event. (See [Section 6.6](#) for the definition of potential DILI.)

Suspected transmission of an infectious agent (eg, pathogenic or nonpathogenic) via the study drug is an SAE.

Although pregnancy, overdose, and cancer are not always serious by regulatory definition, these events must be handled as SAEs. (See [Section 6.1.1](#) for reporting pregnancies).

Any component of a study endpoint that is considered related to study therapy (eg, death is an endpoint, if death occurred due to anaphylaxis, anaphylaxis must be reported) should be reported as SAE (see [Section 6.1.1](#) for reporting details).

NOTE:

The following hospitalizations are not considered SAEs in BMS clinical studies:

- a visit to the emergency room or other hospital department < 24 hours, that does not result in admission (unless considered an important medical or life-threatening event)
- elective surgery, planned prior to signing consent
- admissions as per protocol for a planned medical/surgical procedure
- planned chemotherapy
- routine health assessment requiring admission for baseline/trending of health status (eg, routine colonoscopy)
- medical/surgical admission other than to remedy ill health and planned prior to entry into the study. Appropriate documentation is required in these cases
- admission encountered for another life circumstance that carries no bearing on health status and requires no medical/surgical intervention (eg, lack of housing, economic inadequacy, caregiver respite, family circumstances, administrative reason).

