8.2 Populations for Analyses

- The Randomized/Intent-To-Treat (ITT) population consists of all subjects who were randomized to a treatment, regardless of whether they received study drug or not. Except as noted otherwise, Randomized/ITT Population will be used for the evaluation of efficacy.
- The Modified Intent-To-Treat (mITT) population includes randomized subjects who have either an adjudicated event making up the primary efficacy endpoint or evaluable end of study imaging evaluations, including ultrasound and echocardiogram.
- The Evaluable population will include the Randomized/ITT population except those subjects with relevant protocol deviations expected to affect the primary efficacy endpoint.
- The safety population includes all randomized subjects since there is no intervention on top of standard care in the control arm and will be used for the evaluation of safety.
- The analysis population for pharmacokinetic assessments will include subjects who have received at least one dose of apixaban and have a pharmacokinetic sample collected.
- The analysis population for anti-FXa assessments will include subjects who have received at least one dose of apixaban and have anti-FXa samples collected.

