8.3.2 Secondary Endpoint(s)

Efficacy:

[figure not shown]
- a) Non-fatal asymptomatic DVT
- b) Non-fatal symptomatic DVT
- c) Non-fatal PE
- d) CVST
- e) VTE-related-death

[figure not shown]
Safety

- a) Composite of major and CRNM bleeding (CRNMB). CRNM bleeding is defined as bleeding that satisfies one or both of the following:
 - i) overt bleeding for which blood product is administered and not directly attributable to the subject's underlying medical condition and
 - ii) bleeding that requires medical or surgical intervention to restore hemostasis, other than in an operating room

Pharmacokinetics and Anti-FXa Activity

- a) Apixaban pharmacokinetics using a population pharmacokinetic (PPK) approach
- b) Anti-FXa activity

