7.6 Safety

Safety presentations will be based on the Safety Population during the Treatment Period. In addition to the analyses and summaries based on the Treatment Period, the analyses and summaries for bleeding outcomes, AEs, SAEs, SAEs with death outcome, AEs leading to discontinuation, events of special interest, elevations in liver function tests (LFTs), and decreases in platelet counts will also be performed based on the On-Treatment period for apixaban treated subjects only.

For analyses of events during the Treatment Period, non-serious adverse events will be included in analyses if their onset occurs during the Treatment Period, or within 2 days after the end of the Treatment Period. Serious adverse events will be included in analyses if their onset occurs during the Treatment Period, or within 30 days after the end of the Treatment Period. For analyses of events during the On-treatment Period, events will be included if they occur during the On-treatment period, or within 2 days (non SAE) or 30 days (SAE) after the end of the On-treatment period. All events will be listed.

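### A CRNM bleed judged related to apixaban can be an SAE on that ground alone, a route closed to controls, so the by-arm SAE tables can tilt against apixaban

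*Protocol*

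**What the plan says.** - **Seriousness.** Protocol 6.1 gives the standard list of criteria. A separate sentence then says that "Any component of a study endpoint that is considered related to study therapy" should be reported as an SAE. Its example is a death endpoint caused by anaphylaxis, where the anaphylaxis has to be reported.
- **Relatedness.** Protocol 6 states: "The following categories and definitions of causal relationship to investigational product as determined by a physician should be used for all BMS clinical study AEs". An event is related if "There is a reasonable causal relationship to study drug administration and the AE".
- **Control arm.** Protocol 8.2 notes that "there is no intervention on top of standard care in the control arm". The trial is open-label.
- **Endpoint.** Protocol 8.3.2 and SAP 4.2 make the composite of major and CRNM bleeding the secondary safety endpoint. A bleed can be CRNM because it needed treatment outside the operating room; admission is not required.
- **Tables.** SAP 7.6.2 says: "Summary information (the number and percentage of subjects) regarding AEs (for serious and non-serious events) will be tabulated by SOC, PT and treatment group". The accompanying AE and SAE listing shows relationship, intensity and action taken, but not which seriousness criterion was met.
- **Windows.** SAP 7.6 says: "Serious adverse events will be included in analyses if their onset occurs during the Treatment Period, or within 30 days" of its end. For non-serious events the allowance is 2 days.

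**The concern.** Readers expect a table of related events to depend on who received the drug. They do not expect that of an SAE table, where seriousness is supposed to describe the event and not its attribution. The added sentence in Protocol 6.1 lets attribution decide seriousness, and the attribution is made by someone who knows the arm. CRNM bleeding is where this bites: it is an endpoint component, attribution to an anticoagulant is easy, and some of these bleeds need meet no general criterion. Two clinically identical bleeds can then sit in different tables according to arm. In a trial whose main safety question is bleeding, part of any excess of bleeding SAEs on apixaban could come from the reporting rule, and nothing in the SAP lets a reader see how much.

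**Working it through.** The plan states no figure on this point, so there is none to reproduce. The check is first a reading of the text, then an illustration.

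**Reading the passages together**

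1. The sentence in Protocol 6.1 follows the list of criteria and does not require that any of them be met.
2. It turns on relatedness, which Protocol 6 defines only against the investigational product.
3. Controls receive no investigational product, so a control bleed cannot be related in that sense.
4. CRNM bleeding is a component of a study endpoint, so the literal wording covers it.
5. Control bleeds keep three other routes to SAE status: admission or a longer stay, the important-medical-event criterion (both Protocol 6.1), and the instruction in Protocol 6.1.1 to file an SAE report when seriousness is in doubt. Apixaban bleeds have these routes too.

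The arms therefore differ only for a bleed that takes none of the routes in step 5 and, on apixaban, is called related.

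**Illustration**

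From the documents: about 500 randomized 1:1 (Protocol 8.1), so 500/2 = 250 per arm. Assumed, because the documents give no value:

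- c, the true CRNM rate, equal in both arms, set at 5%;
- s, the share of CRNM bleeds that are SAEs on general grounds, 0.2 to 0.8;
- r, the share of the remaining apixaban CRNM bleeds called related, 0.25 to 1.

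Expected CRNM bleeds classed as SAEs:

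- control = 250 × c × s
- apixaban = 250 × c × [s + (1−s)r]
- ratio = 1 + r(1−s)/s, which does not depend on c

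With 250 × 0.05 = 12.5 CRNM bleeds per arm:

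| s | r | Apixaban | Control | Ratio |
|---|---|---|---|---|
| 0.8 | 0.25 | 12.5 × 0.85 = 10.6 | 10.0 | 1.06 |
| 0.5 | 0.5 | 12.5 × 0.75 = 9.4 | 6.25 | 1.50 |
| 0.2 | 0.5 | 12.5 × 0.60 = 7.5 | 2.5 | 3.00 |
| 0.2 | 1 | 12.5 × 1.00 = 12.5 | 2.5 | 5.00 |
| any | 0 | same as control | 12.5 × s | 1.00 |

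The ratio tends to 1 as s rises or r falls. The last row is what a common rule in both arms would give.

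The non-serious table moves the other way. At s = r = 0.5, apixaban has 12.5 × 0.5 × 0.5 = 3.1 non-serious CRNM bleeds against 6.25 in controls. Totals agree at 12.5 per arm, so the sentence shifts bleeds between tables and, apart from the windows, does not create them.

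**Windows**

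A bleed made an SAE by attribution counts for 30 days after the Treatment Period; the same bleed left non-serious counts for 2. The difference is 30 − 2 = 28 days, and it can only add events on apixaban.

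**The case against.** The strongest reply is that the sentence is not a seriousness criterion at all. Its anaphylaxis example suggests that it is meant to get the drug-related cause behind an endpoint event reported. In addition, study therapy is not defined in 6.1, and Protocol 4 lets study drugs include non-investigational products. This stands as a possible reading, and it is why the point is confined to the literal wording. It does not remove the problem: the sentence is broader than its example, Protocol 6 ties causality to the investigational product, and the roughly 100 sites (Protocol 3.3) could read it differently.

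Second, the overlap with general criteria may be large. The important-medical-event criterion itself mentions medical or surgical intervention, close to one limb of the CRNM definition, and the doubt instruction widens the net further. Most major bleeds would probably be serious anyway. All this raises s and shrinks the effect, but does not bring it to zero while some CRNM bleeds meet no general criterion.

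Third, the longer SAE window should add little. Table 4.5.2-1 expects most of the anticoagulant effect to be gone within 24 hours of the last dose, so few late bleeds should be called related. This stands.

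Fourth, the bleeding comparison proper is protected. Protocol 5.3.1 sends every bleed for adjudication whatever its SAE status, the committee is blinded, and SAP 7.6.1 analyses the adjudicated classes. SAP 7.6.2 specifies no test on SAE counts. This also stands and limits the point to descriptive tables.

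**Conclusion.** The asymmetry is in the text, and the SAP carries it unmarked into the by-arm SAE tables and the two windows. When it acts, it acts against apixaban. Its size cannot be known from the documents: the range of about 1.06 to 5 is correct arithmetic on assumed s and r, and no value within it is an estimate.

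Three stronger conclusions that a reader might infer are not supported.

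- *Every CRNM bleed is an SAE on apixaban and non-serious in controls.* Protocol 6.1 says that such components should be reported, and the difference needs both a related call and no general route. Unrelated apixaban bleeds can stay non-serious, and control bleeds can be SAEs.
- *The safety endpoints are biased.* Major bleeding and the composite with CRNM bleeding rest on blinded adjudication, independent of SAE status.
- *A null effect would necessarily look like excess serious bleeding.* The adjudicated results, and the tables of bleeding-related AEs by arm, would stand beside the SAE counts.

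What remains is a descriptive comparison that can mislead and is cheap to protect.

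**What to change.** Keep every reporting duty in Protocol 6.1 and 6.1.1, and keep the full SAE table. Add to SAP 7.6.2, for example:

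> SAEs that qualify solely because an endpoint component was judged related to study therapy will be flagged. By-arm SAE tables will be shown with and without flagged events, and flagged events will be listed. SAEs falling under any other category in Protocol 6.1, including overdose, pregnancy, cancer and suspected transmission of an infectious agent, are not flagged.

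This is safer than reclassifying flagged events as non-serious, which would downgrade reported SAEs in the drug arm only and could lose late ones under the 2-day rule. The table without flagged events applies the same grounds for seriousness to both arms, which corresponds to the 1.00 row of the illustration.

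The cost is SAP wording, one programming flag and one extra table. The sponsor should confirm that the seriousness criterion met is captured for each SAE; the documents do not show the SAE form. Expedited reporting does not change.
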